### Secondary Objective(s):

- To evaluate the percentage of subjects with SVR12 by formulation, age and weight group and across all subjects on the adult formulations.
- To evaluate the percentage of subjects with SVR24 and the percentage of subjects with ALT normalization by the end of treatment, by formulation, age and weight group, across all subjects, and across all subjects on the adult formulations.

## 5.0 Investigational Plan

### 5.1 Overall Study Design and Plan: Description

In Part 1 of this study eligible HCV GT1-infected, treatment-naïve, non-cirrhotic pediatric subjects will receive OBV, PTV, RTV with DSV and with or without RBV for 12 weeks. Part 2 of this study is a Phase 3 study in which eligible GT1 or 4-infected treatment-naïve or prior IFN (or IFN or pegIFN with or without RBV) treatment-experienced pediatric subjects without cirrhosis or with compensated cirrhosis will receive OBV/PTV/RTV with or without DSV and with or without RBV for 12 or 24 weeks depending on HCV genotype, sub-genotype and cirrhosis status. Part 1 is designed to allow for dose adjustment (details are provided below in *Dose Adjustment Considerations for Part 1*

[*Pharmacokinetic Study*]) on an ongoing basis based on available pharmacokinetic and clinical data to achieve therapeutic exposures that have been demonstrated to be safe and efficacious in adult subjects. Part 2 will evaluate the adult formulations in treatment-naïve and IFN treatment-experienced HCV GT1 or GT4-infected adolescents with or without compensated cirrhosis. Both Parts 1 and 2 will consist of a Screening Period (Section 5.1.1), a Treatment Period (Section 5.1.2), and a 24-week Post-Treatment Period (Section 5.1.3) (Section 5.1.4). Subjects who prematurely discontinue study treatment in Part 1 will be followed in the Post-Treatment Period in Part 1. Similarly subjects who prematurely discontinue study treatment in Part 2 will be followed in the Post-Treatment Period in Part 2. After completing the Post-Treatment Period in Part 1 or Part 2, the subjects will be followed in Part 3 for 144 weeks. Subjects who prematurely discontinue from the Post-Treatment Period in Part 1 or Part 2 or from Part 3 will be discontinued from the study.

### Part 1

In Part 1, the primary objectives are to assess the pharmacokinetics, efficacy and safety of OBV, PTV, RTV and DSV with or without RBV in HCV GT1-infected, treatment-naïve pediatric subjects. Part 1 will include approximately 36 subjects. At least 12 subjects will enroll in each of the 3 age year groups,  $\geq 3$  to 8,  $\geq 9$  to 11, and  $\geq 12$  to 17. Enrollment will begin with pediatric subjects  $\geq 12$  to 17 years old who are  $\geq 45$  kg and willing to swallow the OBV/PTV/RTV and DSV adult formulations. After acceptable pharmacokinetic, efficacy and safety data are available from at least 6 subjects from the  $\geq 12$  to 17 age group who receive the adult regimen, subjects ages  $\geq 9$  to 11 will begin enrollment to be administered the mini-tablet formulations. After acceptable pharmacokinetic, efficacy and safety data are available from at least 6 subjects from the  $\geq 9$  to 11 age group (at least 4 of which have a body weight of 15 to 44 kg) subjects ages  $\geq 3$  to 8 will be enrolled and administered the mini-tablets. In the  $\geq 3$  to 8 year age group, at least 2 subjects each from subgroups  $\geq 3$  to 5 and  $\geq 6$  to 8 years old will be enrolled to ensure that there is adequate information for dosing recommendations for the entire  $\geq 3$  to 8 age group. Up to approximately 12 additional pediatric subjects may be enrolled to

receive the mini-tablet formulation in Part 1 if needed to adequately characterize the pharmacokinetics and determine the final dose strength for a particular age group or subgroup. Subjects will be followed in Part 1 of the study through Post-Treatment Week 24.

In summary, children who are  $\geq 12$  to 17 years old with weight  $\geq 45$  kg and willing to swallow the adult formulations will use the adult formulations of OBV/PTV/RTV with DSV. All other children  $\geq 3$  to 11 years of age will be dosed with the pediatric mini-tablet formulation. For subjects that are not willing to swallow the RBV tablets and are not taking the adult formulations of the DAAs, RBV will be provided as a 40 mg/mL oral solution.

#### *Dose Adjustment Considerations for Part 1*

For each subject, the initial dose of DAAs will be based on the subject's body weight at Screening. No dose adjustments of DAAs or RBV will be made as a consequence of weight change during the treatment period. Dose adjustments may be implemented during the treatment period based on available data and enrollment. When preliminary pharmacokinetic and clinical data (following Week 2 intensive PK sampling or Week 8 trough sample) from approximately 6 subjects in the age group are available, these data will be used to adjust doses, if needed, for subjects who have been enrolled and for subjects who are subsequently enrolled in the respective age group. The data from age groups of  $\geq 3$  to 8 and  $\geq 9$  to 11 years old may be combined for final analyses if exposures from these 2 groups are comparable to each other.

For each of the analytes (OBV, PTV, RTV, or DSV), the geometric mean and individual values of AUC from these pediatric subjects from the Week 2 intensive PK sampling will be compared with the range of geometric means and the range of individual AUCs across Phase 1/2/3 studies in adults that had intensive pharmacokinetic data. Dose adjustments may be made for each component of the DAA regimen if the respective geometric mean AUC in pediatric subjects is outside the geometric mean range in adults and/or at least 2 of 6 pediatric subjects have individual AUCs outside of the individual range in adults. In

addition, if data are available from fewer than 6 subjects and if at least 2 of these subjects have individual AUCs outside of the individual range in adults, dose adjustment might be considered for the age group.

AUC will be the primary measure for dose adjustment.  $C_{max}$  and  $C_{trough}$  will be considered for safety and efficacy using the same rules.

Additional criteria may be considered for making dose adjustment decisions for Part 1 to ensure safe and efficacious exposures. Subjects who take at least one dose of the study drug will be followed in Part 1 of the study through Post-Treatment Week 24 to assess  $SVR_{12}$  and  $SVR_{24}$ .

### Part 2

In Part 2, the primary objectives are to further evaluate the safety and efficacy (percentage of treatment-naïve or treatment-experienced subjects achieving  $SVR_{12}$ ) of OBV/PTV/RTV and DSV with or without RBV in HCV GT1-infected pediatric subjects and OBV/PTV/RTV in GT4-infected pediatric subjects with or without compensated cirrhosis. Part 2 will enroll approximately 16 HCV GT1-infected and 10 GT4-infected, treatment-naïve or IFN (IFN or pegIFN with or without RBV) treatment-experienced pediatric subjects ages  $\geq 12$  to 17 years of age. Enrollment in Part 2 will begin once dosing recommendations of OBV, PTV, RTV and DSV are available for the  $\geq 12$  to 17 year-old age group based on the pharmacokinetic and clinical data from Part 1 of the study. Subjects who take at least one dose of the study drug will be followed in Part 2 of the study through Post-Treatment Week 24 to assess  $SVR_{12}$  and  $SVR_{24}$ .

### Part 3 (Long-Term Follow-Up Period)

In Part 3, the objectives are to assess the durability of response for subjects who achieved SVR, to assess the persistence of specific HCV amino acid variants associated with drug resistance in subjects who experienced virologic failure and to assess the impact of OBV/PTV/RTV with or without DSV co-administered with or without RBV on growth and development. All pediatric subjects who complete the PT Week 24 visit in Part 1 or

Part 2 will be automatically enrolled into Part 3 and followed for up to 144 weeks. Subjects will return to their study site for their scheduled visits on an outpatient basis. Subjects with virologic failure are allowed to use any other approved treatments for their HCV infection, if appropriate, while participating in the Long-term Follow-up study; however that therapy would be provided outside the context of this study and needs to be captured in source documents and entered into EDC by site personnel.

#### Fibrosis Assessment

An assessment of liver fibrosis is mandatory prior to enrollment. Subjects, with no history of cirrhosis, who have not had a liver biopsy or FibroScan within 24 months prior to screening, will undergo a non-invasive FibroTest to determine presence or absence of cirrhosis.

Subjects will be considered to be non-cirrhotic based on a liver biopsy within 24 months prior to screening demonstrating the absence of cirrhosis (e.g., a Metavir Score of 3 or less, Ishak score of 4 or less) or, if a liver biopsy is unavailable, a historical Fibroscan® result < 14.6 kPa within 24 months prior to screening. If neither historical result is available, a screening FibroTest score of < 0.75 can be used to demonstrate absence of cirrhosis.

Subjects will be considered to have cirrhosis based on previous histologic diagnosis of cirrhosis on a liver biopsy at any time prior to screening (e.g., Metavir Score of > 3 [including 3 – 4 or 3/4], Ishak score of > 4) or, if a liver biopsy is unavailable, a historical FibroScan score  $\geq$  14.6 kPa or a screening FibroTest  $\geq$  0.75 (Table 4).

**Table 4. Baseline Fibrosis Stage**

Baseline Fibrosis Stage, Metavir Equivalents	Liver Biopsy Metavir, Batts-Ludwig, Knodell, IASL, Scheuer, or Laennec Score	Liver Biopsy Ishak Score	FibroScan (kPa)	FibroTest
F0 – F1	0 or 1	0, 1, or 2	< 8.8	< 0.49
F2	2	3	≥ 8.8 to < 9.6	0.49 to < 0.59
F3	3	4	≥ 9.6 to < 14.6	0.59 to < 0.75
F4	4	5 or 6	≥ 14.6	≥ 0.75

The resulting fibrosis status (F0-F3 noncirrhotic, F4 cirrhotic) and HCV genotype/sub-genotype will be documented via recording in the Interactive Response Technology (IRT) system for each subject to determine the duration and regimen of the study drug for each subject.

Subjects will be considered treatment-naïve if they have never received any antiviral treatment for hepatitis C virus infection.

[figure not shown]
Subjects will be considered treatment-experienced if they have received prior IFN (IFN or pegIFN with or without RBV) excluding DAAs. Subjects with prior treatment with IFN will be categorized as one of the following:

- Non-responder: HCV RNA detected at the end of a prior IFN, IFN/RBV or pegIFN/RBV treatment course (except for breakthrough, which is captured separately). These subjects are further categorized as:
  - Null-responder: failed to achieve a 1 log10 IU/mL reduction in HCV RNA by Week 4 or a 2 log10 IU/mL reduction in HCV RNA by Week 12 during a prior IFN, IFN/RBV or pegIFN/RBV treatment course;
  - Partial responder: achieved at least 2 log10 IU/mL reduction in HCV RNA by Week 12 during a prior IFN, IFN/RBV or pegIFN/RBV treatment course but failed to achieve HCV RNA undetectable at the end of treatment;

- Unknown or unable to specify: insufficient data to categorize as null or partial responder.
- Breakthrough: confirmed  $\geq 1 \log_{10}$  IU/mL increase from nadir or achieved HCV RNA undetectable (or unquantifiable) during a prior IFN, IFN/RBV or pegIFN/RBV treatment course but HCV RNA was quantifiable during or at the end of treatment.
- Relapser: achieved HCV RNA undetectable at the end of a prior IFN, IFN/RBV or pegIFN/RBV treatment course but HCV RNA was detectable following cessation of therapy.
- Unknown/other IFN-experienced: subject received a prior IFN, IFN/RBV or pegIFN/RBV treatment course and reason for not achieving SVR is unknown or other than above.

After meeting the eligibility criteria, subjects will be enrolled to 12 weeks of treatment in Part 1 or either 12 or 24 weeks of treatment in Part 2.

**Figure 1. Study Schematic**

The study is designed to enroll approximately 62 subjects to meet scientific, regulatory and clinical objectives without enrolling an undue number of subjects in alignment with

ethical considerations. Therefore, if the target number of subjects has been enrolled, there is a possibility that additional subjects in screening will not be enrolled.

### **5.1.1 Screening**

At the Screening Visit for Part 1 or Part 2, parent(s)/guardian(s) must provide written (signed and dated) informed consent and the subject must provide assent (as appropriate for age and country) respectively, prior to any study specific procedures on the subject.

Subjects will receive a unique subject number via the IRT system and will undergo the study procedures identified in Section 5.3.1 associated with the Screening Visit. The investigator or his/her designated and qualified representatives will evaluate whether the subject meets all of the eligibility criteria specified in Section 5.2.1 and Section 5.2.2 for the Part in which they are enrolling during the period from the Screening Visit through Study Day 1 prior to dosing and record the results of this assessment and the details of the informed consent and assent process in the subject's medical records.

Eligible subjects have up to 42 days following the Screening Visit to enroll into Part 1 or Part 2 of the study. There is no screening period for Part 3 (Long-term Follow-up). Part 3 will start the day after the PT Week 24 Visit in Part 1 or Part 2.

#### **5.1.1.1 Rescreening**

Subjects who have any of the following results are ineligible to rescreen or have other exclusionary laboratory parameters retested: an exclusionary HCV genotype, a positive hepatitis B surface antigen (HBsAg), positive human immunodeficiency virus (HIV) antibody or confirmed pregnancy.

Subjects who meet all eligibility criteria with the exception of **up to three (3)** exclusionary laboratory parameters may repeat laboratory testing once within the 42-day screening period without prior AbbVie approval. Subjects being retested because of exclusionary laboratory parameter(s) must have the related panel(s) repeated

(e.g., bilirubin requires a repeat chemistry panel) within the same screening period and all eligibility criteria must be met on the repeated panels.

**Subjects may be rescreened only once as follows:**

- Subjects who have more than 3 exclusionary laboratory results require approval from the AbbVie Therapeutic Area Medical Director prior to rescreening.
- Eligible subjects who fail to enroll within 42 days of screening, regardless of the reason for falling outside the 42-day screening window.

For subjects who do not meet the study eligibility criteria, the site personnel must register the subject as a screen failure in both IRT and electronic data capture (EDC) systems.

**5.1.2 Treatment Period (TP)**

After meeting all the eligibility criteria, subjects will be enrolled to a study regimen according to their HCV sub-genotype for Part 1 (Table 5) or to a study regimen and study duration according to their HCV genotype, sub-genotype and cirrhosis status in Part 2 (Table 6).

**Table 5. Treatment Regimen and Duration – Part 1**

Patient Population	Treatment	Duration
Genotype 1b, without cirrhosis	ombitasvir + paritaprevir + ritonavir + dasabuvir	12 weeks
Genotype 1a,* without cirrhosis	ombitasvir + paritaprevir + ritonavir + dasabuvir + ribavirin	12 weeks

\* Follow the genotype 1a dosing recommendations in patients with an unknown genotype 1 sub-genotype or with mixed genotype 1 infection.

In Part 1, treatment-naïve HCV GT1-infected subjects without cirrhosis will receive OBV, PTV, RTV and DSV with or without RBV for 12 weeks according to Table 5. In Part 2, HCV GT1 and GT4-infected subjects with and without compensated cirrhosis who are either treatment-naïve or previously treated with IFN (IFN or pegIFN with or without

RBV) will receive OBV/PTV/RTV with or without DSV and with or without RBV according to [Table 6](#). The treatment duration will be 12 or 24 weeks depending on their genotype, subgenotype and cirrhosis status. Details regarding enrollment in Part 1 and Part 2 are outlined in [Section 5.1](#) (Overall Study Design and Plan: Description).

**Table 6. Treatment Regimen and Duration – Part 2 (For Subjects ≥ 12 – 17 Years of Age)**

Patient Population	Treatment	Duration
Genotype 1b with or without compensated cirrhosis	ombitasvir + paritaprevir + ritonavir + dasabuvir	12 weeks
Genotype 1a,* without cirrhosis	ombitasvir + paritaprevir + ritonavir + dasabuvir + ribavirin	12 weeks
Genotype 1a,* with compensated cirrhosis	ombitasvir + paritaprevir + ritonavir + dasabuvir + ribavirin	24 weeks
Genotype 4 with or without compensated cirrhosis	ombitasvir + paritaprevir + ritonavir + ribavirin	12 weeks

\* Follow the genotype 1a dosing recommendations in patients with an unknown genotype 1 sub-genotype or with mixed genotype 1 infection.

The site will enter subject's genotype and sub-genotype (GT1b/GT1 non-b/GT4) and fibrosis stage in the IRT system in order to obtain the subject's treatment regimen and duration.

OBV, PTV, RTV, DSV (if applicable) and RBV (if applicable) will be administered as described in [Section 5.5.1](#) (Treatments Administered). Subjects and their parent(s)/guardian(s) will receive instructions about the study drugs at the Day 1 Visit. The study drugs will be dispensed at the visits as indicated in [Appendix C](#).

After enrollment, all subjects will continue to return to the site on an outpatient basis for the study visits and procedures as identified in [Appendix C](#). Subjects could also return to the site for an unscheduled study visit for additional safety assessments if the investigator feels it is necessary. Sites should ensure that subjects adhere to the study visits listed in [Appendix C](#). Subjects who cannot complete their study visit per the visit schedule should

ensure they do not run out of study drug prior to their next study visit. Compliance is critical to ensure adequate drug exposure.

Virologic failure criteria will be evaluated and applied by the Investigator as detailed in Section 5.4.3.

Subjects who prematurely discontinue from the Treatment Period should return for a Treatment Discontinuation Visit and undergo the study procedures as outlined in [Appendix C](#) and as described in Section 5.3.1.1. Ideally, this should occur on the day of study drug discontinuation, but is recommended to be no later than 2 days after their final dose of study drug and prior to the initiation of any other anti-HCV therapy if applicable. Following completion or premature discontinuation of study drug treatment, all subjects in either Part 1 or Part 2 will be followed in the associated Post-Treatment Period of Part 1 or Part 2.

### **5.1.3 Post-Treatment Period of Part 1 and Part 2**

All subjects who receive at least one dose of the study drug will enter into the Post-Treatment Period of Part 1 or Part 2. The 24-week Post-Treatment Period of Parts 1 and 2 will include the visits through Post-Treatment Week 24 as outlined in [Appendix C](#). Subjects who prematurely discontinue during the Post-Treatment Period should return to the site for a discontinuation visit and undergo the study procedures as outlined in [Appendix C](#).

### **5.1.4 Long-Term Follow-Up Period**

All subjects who complete the Post-Treatment Week 24 visit will automatically be enrolled into Part 3 – the Long-term Follow-up Period and return to the site on an outpatient basis for the study visits and procedures as identified in [Appendix C](#). The Long-term Follow-up Period will begin the day following the Post-Treatment Week 24 visit and last for 144 weeks as outlined in [Appendix C](#). Subjects may also return to the site for an unscheduled study visit for additional safety assessments if the investigator feels it is necessary.

The Long-term Follow-up Period will assess safety, antiviral response, and growth and development.

Growth and development will be assessed using waist circumference, Tanner Pubertal Staging, height standardized score, and growth rate defined as the change in height over change in age from the previous visit.

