## 1.2 Synopsis

AbbVie Inc.	Protocol Number: M14-748
Name of Study Drug: ombitasvir, paritaprevir, ritonavir, dasabuvir, ribavirin	Phase of Development: 2/3
Name of Active Ingredient: ombitasvir, paritaprevir, ritonavir, dasabuvir, ribavirin	Date of Protocol Synopsis: 21 August 2017
Protocol Title: An Open-Label, Multicenter Study to Evaluate the Pharmacokinetics, Safety, and Efficacy of Ombitasvir (OBV), Paritaprevir (PTV), Ritonavir (RTV) With or Without Dasabuvir (DSV) and With or Without Ribavirin (RBV) in Pediatric Subjects With Genotype 1 or 4 Chronic Hepatitis C Virus (HCV) Infection (ZIRCON)	
Objectives: To assess the pharmacokinetics of OBV, PTV, RTV, and DSV with or without RBV in treatment-naïve, non-cirrhotic, HCV GT1-infected pediatric subjects in Part 1. To assess the efficacy (percentage of subjects achieving SVR 12 [defined as HCV RNA < LLOQ 12 weeks after the last actual dose of study drug]) or SVR 24 [defined as HCV RNA < LLOQ 24 weeks after the last actual dose of study drug]) and safety of OBV, PTV, RTV with or without DSV and with or without RBV for 12 or 24 weeks in HCV genotype 1 (GT1) or genotype 4 (GT4)-infected treatment-naïve and prior IFN (IFN or peg-IFN with or without RBV) treatment-experienced, cirrhotic and non-cirrhotic pediatric subjects in Part 1 and Part 2. To assess the durability of response for subjects who achieved SVR, to assess the emergence and persistence of specific HCV amino acid variants associated with drug resistance in subjects who experienced virologic failure, and to assess the impact of OBV, PTV, RTV with or without DSV and with or without RBV on growth and development in Part 3, the long-term follow-up of approximately 2.5 years.	
Investigator: Global, multicenter trial: Investigator information is on file at AbbVie.	
Study Sites: Up to 30 sites globally.	
Study Population: Part 1: Treatment-naïve, non-cirrhotic, GT1-infected pediatric patients ≥ 3 to 17 years of age Part 2: Treatment-naïve and IFN (IFN or peg-IFN with or without RBV) treatment-experienced HCV GT1 or GT4-infected pediatric subjects ≥ 12 to 17 years of age with or without compensated cirrhosis Part 3 (Long-term follow-up): All subjects who take at least one dose of study drug and complete the Post-Treatment (PT) Week 24 visit in Part 1 or Part 2.	

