**Figure 1. Study Schematic**

The treatment duration will be 12 weeks for all subjects except HCV GT1a-infected subjects with cirrhosis; these subjects will receive treatment for 24 weeks.

The duration of the study will be 156 weeks (for subjects receiving a 12-week treatment) or 168 weeks (for subjects receiving a 24-week treatment), not including a screening

period of up to 42 days, consisting of a 12-week or 24-week Treatment Period and a Post-Treatment (PT) Period of 144 weeks in total for all subjects who receive at least one dose of study drug.

Subjects who meet the eligibility criteria will be enrolled in Part 1 or Part 2 to either 12 or 24 weeks of combination therapy with or without RBV based on HCV genotype, subtype, and cirrhosis status as described in [Table 1](#).

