### **Post-Treatment Period**

All subjects who receive at least one dose of study drugs will be monitored for an additional 24 weeks following the last dose of study drugs in Part 1 or Part 2. All subjects who complete the PT Week 24 visit in Part 1 or Part 2 will be followed till PT Week 144 in Part 3.

The Post-Treatment (PT) Period will include assessment of antiviral response, growth and development outcomes (assessed by height and tanner pubertal stage), patient reported outcomes (assessed by EuroQol 5 Dimensions 3 Levels Health State Instrument [EQ-5D-3L] questionnaire), HCC (assessed by liver ultrasound only for subjects with cirrhosis), and progression of liver disease (assessed by Fibrotest).

The PT Period will begin the day following the last dose of study drug treatment.

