#### **4.4                   Planned Analysis**

An interim analysis will occur after all subjects in Part 1 or Part 2 have completed the PT Week 12 Visit or prematurely discontinued from study. The database will be versioned after performing appropriate data cleaning. Final data through PT Week 144 will be locked in a later version of the database. SAS® (SAS Institute, Inc., Cary, NC) for the UNIX operating system will be used for all analyses. All statistical tests and all confidence intervals will be two-sided with an  $\alpha$  level of 0.05.

All analyses will be conducted by statisticians and statistical programmers at AbbVie or their designees according to the methodologies specified in this SAP.

There is no intention of changing the study design based on efficacy findings from the PT Week 12 interim analysis. The intention is to follow all subjects who receive study drug for at least 144 weeks following treatment. There will be no statistical adjustment employed due to this interim analysis.

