### **Missing Data Imputation for SVR**

HCV RNA values will be selected for analysis based on the analysis windows defined in Section 6.3.

For analyses of SVR, subjects' missing visit values will have backward imputation applied, if possible. For backward imputation, if the nearest HCV RNA value after the SVR window is unquantifiable or undetectable, then it will be used to impute the HCV RNA value in the SVR window. If a subject is missing an HCV RNA value within the appropriate SVR window after performing backward imputation, then this value will be imputed with an HCV RNA value from a local laboratory if present; otherwise, the HCV RNA value will be missing. Subjects with missing HCV RNA data in the analysis window, after imputations, will be imputed as a failure.

Regardless of the imputation method described above, if a subject starts another treatment for HCV, then all HCV RNA values for this subject measured on or after the start date of the new HCV treatment will be excluded from analyses. The subject will be considered a failure for summaries of viral response at all time points after the start of the new HCV treatment.

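### Part 3 is open only to children who complete the PT Week 24 visit, while the SAP promises 144 weeks of follow-up for every dosed child; a child who misses that visit without withdrawing has no stated route onward

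*Protocol*

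**What the plan says.** **Condition for Part 3.** The protocol synopsis (Study Population) defines Part 3 as subjects who took at least one dose and who "complete the Post-Treatment (PT) Week 24 visit in Part 1 or Part 2". The synopsis methodology and sections 5.1 (Part 3) and 5.1.4 repeat the link to that visit; 5.1.4 reads "All subjects who complete the Post-Treatment Week 24 visit will automatically be enrolled into Part 3". The start date hangs on the same visit: section 5.1.1 says "Part 3 will start the day after the PT Week 24 Visit in Part 1 or Part 2", and the Definition of Terms in section 1.3 agrees. Section 8.1 defines ITT-3 as the subjects who enter Part 3, so ITT-3 inherits the condition.

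**What the SAP says.** The text under Figure 1 in SAP 4.2 gives a "Post-Treatment (PT) Period of 144 weeks in total for all subjects who receive at least one dose of study drug". SAP 4.4 adds: "The intention is to follow all subjects who receive study drug for at least 144 weeks following treatment". Yet the Post-Treatment Period paragraph of SAP 4.2 says "All subjects who complete the PT Week 24 visit in Part 1 or Part 2 will be followed till PT Week 144 in" Part 3, and an earlier paragraph of 4.2 places Part 3 after completion of the Post-Treatment Period.

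**Leaving the study.** Protocol 5.1 says "Subjects who prematurely discontinue from the Post-Treatment Period in Part 1 or Part 2 or from Part 3 will be discontinued from the study". Neither document says what happens to a child who misses PT Week 24 and does not withdraw.

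**Missing SVR24.** Under SAP 6.3 an empty SVR window is filled by a later sample "if the nearest HCV RNA value after the SVR window is unquantifiable or undetectable"; failing that, by a local laboratory value; failing that, the child is a failure. Protocol 8.1 has a similar rule.

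**The concern.** Part 3 exists to measure durability of response, persistence of resistant variants, and growth. Admission by attendance at one particular visit selects the cohort on attendance, and the SAP's two statements about all dosed children cannot then be met.

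The same condition reaches SVR24. The next scheduled HCV RNA sample after the SVR24 window is PT Week 36, which is a Part 3 visit. A child kept out of Part 3 does not have the scheduled sample that could fill the gap, so non-attendance may be counted as loss of response. SVR24 is compared with 67% in the sequential procedure of SAP 10.2. It also enters the SVR12/SVR24 concordance and positive predictive value in SAP 10.4, where such a child would appear as SVR12 achieved and SVR24 not achieved.

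**Working it through.** **Inputs.** Planned total about 62 (protocol synopsis; SAP 4.2). Response assumed for sample size 90%, threshold 67%, two-sided 95% interval (SAP 4.3, 10.4). Wilson score interval (SAP 10.3.2). SVR24 window: study drug end days 127 to 210; PT Week 36 window: 211 to 294 (SAP Table 3). Visit schedule: protocol Appendix C.

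**The plan's own figures.** SAP 4.3 states more than 90% power with 50 subjects. Take the smallest responder count r whose lower bound exceeds 67%, then P(X ≥ r) for a binomial with p = 0.90:
- normal approximation: r = 40, power 99.1%;
- Wilson: r = 41, power 97.5%.

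The statement reproduces. The SAP durations also reproduce as 12 + 144 = 156 and 24 + 144 = 168 weeks, so they do assume 144 weeks for each child.

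**Path of a child who misses PT Week 24 without withdrawing, on the literal reading.**
1. The visit is not completed, so the synopsis definition of Part 3 is not met, and Part 3 has no start date.
2. PT Weeks 36, 48, 96 and 144 fall away: 4 HCV RNA visits. Post-treatment heights are scheduled at PT Weeks 12, 36, 96 and 144, so 3 of 4 are lost.
3. No value lies in days 127 to 210, and no scheduled sample falls after day 210.
4. Without an unscheduled source, SVR24 is imputed as failure.

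**Effect on SVR24.** One responder counted as a failure costs 1/62 = 1.6 points. The Wilson lower bound is

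L = [p + z²/(2n) − z√(p(1−p)/n + z²/(4n²))] / (1 + z²/n), with n = 62 and z = 1.96.

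For 56/62, p = 0.9032: L = (0.9032 + 0.0310 − 0.0798)/1.0620 = 80.5%.

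The documents give no missed-visit rate, so the numbers of skips below are assumptions. Each skip is a true responder with no fallback value.

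| Skips | SVR24 | Wilson lower bound |
|---|---|---|
| 0 | 56/62 = 90.3% | 80.5% |
| 1 | 55/62 = 88.7% | 78.5% |
| 3 | 53/62 = 85.5% | 74.7% |
| 6 | 50/62 = 80.6% | 69.1% |

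The test needs at least 49/62 (lower bound 67.4%); 48/62 gives 65.6%. From 56 responders, 56 − 49 = 7 skips can be absorbed.

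**The same in terms of power.** Let the number of responders vary and assume that a share m of children skip with no fallback. The observed rate is then 0.90 × (1 − m). With n = 62 and r = 49, power is 99.7% at m = 0, 94.2% at 5%, 71.9% at 10% and 38.4% at 15%. If true SVR24 is 95%, the last three become 99.8%, 94.2% and 70.1%.

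**The case against.** A reader might infer that one skipped visit ends follow-up and disables backward imputation for SVR24. The documents do not support that.

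- The sentence in 5.1.4 taken alone is a sufficient condition: it says who is enrolled automatically, not that nobody else may be. The restriction comes from the synopsis definition and from the start date tied to the visit.
- No section equates a missed visit with discontinuation. The exit rule in protocol 5.1 covers premature discontinuation only. Loss from follow-up is the literal consequence of silence, and sites could act differently.
- Backward imputation still works in several cases. If the visit took place but the HCV RNA result is missing, the child enters Part 3 and PT Week 36 supplies a value. The window is 84 days wide (210 − 127 + 1), so a delayed visit often still falls inside it, and a visit completed after day 210 can be imputed back. A child treated as discontinued should return for a discontinuation visit (protocol 5.1.3), for which Appendix C schedules HCV RNA. A local laboratory value is a further fallback.
- The rule is written for SVR in general, not for a skipped PT Week 24 visit. For the primary SVR12 endpoint, PT Week 24 is itself a source.
- It is also not simply protocol against SAP, since SAP 4.2 carries the entry condition too.
- Counting missing as failure is a stated, conservative rule, and SAP 10.1 reports missing data as its own category of non-response.

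All of this stands, and it narrows the SVR24 effect to children with no value from any of these sources. It does not remove the contradiction between the two documents and within SAP 4.2, nor supply a route into Part 3 for a child still participating.

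**Conclusion.** The concern holds in a limited form. The entry condition is explicit, it conflicts with two statements in the SAP, and followed literally it excludes a participating child from Part 3 and ITT-3 for one missed visit.

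The harm is mainly a downward-biased SVR24 estimate (1.6 points for each affected responder) and a long-term cohort selected on attendance. At the planned response, a few skips would not fail the 67% comparison: six still leave 69.1%. Power would suffer materially only if about 10% or more of children had no usable value, which is an assumed rate and not one the documents give. The primary SVR12 endpoint is not directly affected. The change is worth making because it is cheap and protects data that the SAP already expects to have.

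**What to change.** 1. Let every dosed subject who has not withdrawn from the study continue to the Part 3 visits, whether or not the PT Week 24 visit took place.
2. Define the Part 3 start by study drug end day: for example, the day after the PT Week 24 visit or, if it is missed, the day after the SVR24 window closes at day 210. PT Week 36 (days 211 to 294) is then available to fill an empty SVR24 window.
3. Define ITT-3 the same way.
4. Align the protocol synopsis (Study Population, Methodology, Part 3), the Definition of Terms in 1.3, and sections 5.1, 5.1.1, 5.1.4 and 8.1. In SAP 4.2, align the design text and the Post-Treatment Period paragraph with the text under Figure 1 and with SAP 4.4.

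If the sponsor does want the present condition, the text under Figure 1 and SAP 4.4 must be changed to match it. That removes the contradiction but keeps the loss of data.

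Cost: a short amendment touching several sections, and a few more scheduled visits. The longest course is 6 weeks of screening + 24 of treatment + 144 of follow-up = 174 weeks, about 40 months, which is within the 42 months that inclusion criterion 2 already asks of families. Children who withdraw will still be lost.
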